#### 810 **10.9.2 Suspending/Stopping Overall Study**

811 In the case of an unanticipated system malfunction resulting in a severe hypoglycemia or severe  
812 hyperglycemia event (as defined in section 10.2.2), use of the study device system will be  
813 suspended while the problem is diagnosed.

814 In the event that two distinct episodes of DKA, two distinct severe hypoglycemia events, or one  
815 distinct DKA episode and one distinct severe hypoglycemia episode, as defined in section 10.2  
816 occur, the overall study would be suspended while the underlying conditions are determined.

817 In addition, study activities could be similarly suspended if the manufacturer of any constituent  
818 study device requires stoppage of device use for safety reasons (e.g. product recall). The affected  
819 study activities may resume if the underlying problem can be corrected by a protocol or system  
820 modification that will not invalidate the results obtained prior to suspension. The Medical Monitor  
821 may request suspension of study activities or stoppage of the study if deemed necessary based on  
822 the safety data available.

### 823 **10.10 Independent Safety Oversight**

824 Detailed in Chapter 7.

### 825 **10.11 Definition of a Data Breach**

826 A data breach is defined in the HITECH Act (43 USC 17932) as an unauthorized acquisition,  
827 access, or use of protected health information (PHI) that compromises the security or privacy of  
828 such information.

829

## 830 **Chapter 11 Miscellaneous Considerations**

### 831 **11.1 Prohibited Medications, Treatments, and Procedures**

832 Participants using insulins other than lispro and aspart at the time of enrollment will be asked to  
833 contact their personal physician to change their prescribed personal insulin to lispro or aspart for  
834 the hotel sessions of the trial.

835 The study devices (study insulin pump, study CGM) must be removed before Magnetic Resonance  
836 Imaging (MRI), Computed Tomography (CT) or diathermy treatment. Participants may continue  
837 in the trial after temporarily discontinuing use if requiring one of the treatments above.

### 838 **11.2 Participant Withdrawal**

839 Participation in the study is voluntary. Participant may withdraw at any time. For participants who  
840 do withdraw from the study, the study team will determine if their data will be used in analysis.

### 841 **11.3 Confidentiality**

842 For security and confidentiality purposes, subjects will be assigned an identifier that will be used  
843 instead of their name. De-identified subject information may also be provided to collaborators  
844 involved in the study after the appropriate research agreement has been executed.

## 845 Chapter 12 Statistical Consideration

### 846 12.1 Design and Randomization

847 This is an early study intending to pilot test the safety and feasibility of a NAP implementation of  
848 an established AP controller – UMPC – in a crossover design (Figure 1).

849 The randomization list will use a sequence of computer-generated pseudorandom Bernoulli trials  
850 and will aim to balance age/gender and match groups by baseline HbA1c. The two groups will  
851 follow two different sequences of AID approaches: NAP followed by UMPC or UMPC followed  
852 by NAP.

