# CLINICAL PROTOCOL

## PROTOCOL SUMMARY

PROTOCOL SECTION	DESCRIPTION
Title	Adaptive Motif-Based Control (AMBC): Pilot 1 – Neural Net Implementation of Automated Insulin Delivery
Investigational Devices	Neural Net Artificial Pancreas (NAP) implementation of the UVA model predictive control algorithm (UMPC); Both NAP and UMPC are investigational devices.
Objectives	The purpose of this study is to test the safety and feasibility of a neural net implementation of an established AP controller, known as UMPC, previously approved by IDE G200206, and tested in the following randomized controlled clinical trials: ClinicalTrials.gov NCT04545567, NCT04877730, and NCT05528770.
Study Design	A randomized cross-over trial assessing glycemic control on NAP, compared to the original UMPC algorithm, which includes two sessions studied in a supervised hotel setting: 1) using NAP – a neural net implementation of UMPC, and 2) using the original UMPC without modifications (see IDE G200206).
Number of Sites	One
Endpoint	The primary outcome will be time in range 70-180 mg/dL for an 18-hour period, 6 PM to 12 PM on the next day, including dinner and breakfast meals.
Population	Key Inclusion Criteria 

• Age <math>\geq</math>18 years of age

• Clinical diagnosis, based on investigator assessment, of type 1 diabetes for at least 1 year

• Currently using insulin for at least six months

• Currently using the Control-IQ (CIQ) automated insulin delivery (AID) system.

Sample Size	Up to 20 participants
Treatment Groups	Randomized crossover: Participants will be randomized to two groups differing by the order of controller use: Group A: NAP first followed by UMPC; Group B: UMPC followed by NAP.
Participant Duration	Up to 6 weeks: Participants will be studied at a local hotel or rental house to test two algorithms, approximately 20 hours per each test. Prior to each hotel session, participants will passively collect CIQ data for a week. The two hotel sessions can be performed sequentially during the same hotel stay or in two hotel stays separated up to 28 days.

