### 148 **1.5 Hotel Sessions**

149 The participants will arrive to hotel and the experimental system will be set up and started within  
150 approximately two hours before dinner: participant's CIQ will be replaced by a Tandem research  
151 pump connected to the DiAs platform and their Dexcom G6 Transmitter will be linked with DiAs.  
152 The research pump will be programmed based on the individual's usual insulin parameters. Once  
153 started, the participants will have their blood sugar managed through this system during 18 hours  
154 of the time at hotel. A pre-meal bolus using the participant's normal insulin-to-carbohydrate ratio  
155 (ICR) will occur for dinner and breakfast after initiating the experimental system. Each participant  
156 will have two of these sessions: one on NAP and one on UMPC, in random order, separated by 0-  
157 28 days. In particular, the two hotel sessions can be combined into one, with two 18-hour periods  
158 alternating NAP vs UMPC. (see Figure 1).

159 During these 18-hour hotel sessions participants will be followed to compare blood glucose control  
160 on NAP vs. UMPC. The study meals and activities will be kept the same between study sessions.  
161 Study staff who will be present will include nursing and technical staff; a study physician/nurse  
162 practitioner/physician's assistant will be available either on-site or nearby off-site. Hyperglycemia  
163 and hypoglycemia treatment protocols will be followed per guidelines. UVa CDT study staff will  
164 monitor CGM output continuously and manage glucose control issues. At the end of the hotel stay,  
165 the participant will return to their home insulin management.

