# CLINICAL PROTOCOL

## 370 **Chapter 6 Hotel Session**

### 371 **Visit 3 and 5**

372 Each participant will have two hotel sessions. Each session will be of approximately 20 hours  
373 duration (see Figure 1). The sessions may occur sequentially within the same hotel stay or within  
374 28 days of each other. If the hotel sessions are sequential, it is not required that the initial hotel  
375 check-procedures procedures be repeated.

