### 400 **6.2 Session Check-In**

401 Participants will arrive at the hotel around 4PM, approximately 2 hours before dinner. The study  
402 team will perform vital signs and inquire about any changes to the participant's medical history.  
403 Any changes to medical history will be communicated to the medical physician to ensure  
404 continued eligibility and participation.

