## CLINICAL PROTOCOL

442 until ketone concentration is  $\leq 0.6$  mmol/L. Closed-loop control using DiAs will be re-initiated  
443 once the participant's CGM reading is  $< 250$  mg/dL and ketones are  $< 0.6$  mmol/L. If ketone  
444 concentration is  $> 1.0$  mmol/L with significant symptoms, the study physician will recommend the  
445 appropriate medical treatment and the participant will be withdrawn from that portion of the study  
446 (the participant may possibly reinitiate the hotel portion of the study at a later date if a reversible  
447 cause)

448 **6.4 Study Meals**

449 Participants will eat dinner and breakfast during the session, with approximately the same amount  
450 of carbohydrate, protein, and fat for Sessions 1 and 2. Snacks with carbohydrates will not be  
451 allowed unless for the treatment of low blood sugars. Non-carbohydrates snacks may be allowed  
452 throughout the protocol per investigator discretion. Study staff will assist with bolusing decisions  
453 prior to all meals.

454 **6.5 Hotel Activities**

455 Generally, the daily routine of the participant will follow their usual daily routine as close as  
456 possible. Exercise will be permitted, to the extent it is typical for the participant and feasible for  
457 study staff to remotely monitor (e.g. would not allow a run outside).

458 If the hotel sessions are sequential within the same hotel stay, then the system algorithm will be  
459 changed by study staff to the second randomized condition at approximately 1 pm on the second  
460 day and the check-in procedures in section 6.2 do not need to be repeated. The hotel activities  
461 during the second session will be the same as the first (i.e. identical timing and content of meals,  
462 identical timing of activities).

463 **6.6 Hotel Discharge**

464 Discharge will be at approximately 1 pm. Discharge criteria is CGM value between 80-250 mg/dL  
465 with stable trend and ketones  $\leq 0.6$  mmol/L. If the CGM values are above 250 mg/dL and ketone  
466 values are  $> 0.6$  mmol/L, the study team will check the insulin pump infusion site and correction  
467 insulin will be administered per study physician judgement via the subject's insulin pump. The  
468 participant will not be able to be discharged from the study until the discharge criteria are met. The  
469 participant's CIQ will be reactivated and a qualified clinical study team member (e.g. MD, NP,  

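### Section 12.1 aims at covariate balance through Bernoulli draws with no mechanism and leaves sequence balance to chance; blocked sequences and a stated period-adjusted estimator would remove a usually small chance error

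*Combined protocol and SAP*

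**What the plan says.** Section 12.1 describes the allocation in one sentence: "The randomization list will use a sequence of computer-generated pseudorandom Bernoulli trials" "and will aim to balance age/gender and match groups by baseline HbA1c". The two sequences are NAP then UMPC, and UMPC then NAP. The success probability of the draws, the intended ratio, and any blocks, strata, minimisation or covariate-dependent rule are not given. Chapter 4 adds only that the order is random and that screening failures and dropouts may be replaced; it does not say which sequence a replacement receives.

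On timing, the Protocol Summary states: "The two hotel sessions can be performed sequentially during the same hotel stay or in two hotel stays separated up to 28 days". Chapter 6 repeats the choice ("The sessions may occur sequentially within the same hotel stay or within" 28 days of each other). Under 6.2, "Participants will arrive at the hotel around 4PM, approximately 2 hours before dinner". Under 6.5, in a sequential stay the algorithm is "changed by study staff to the second randomized condition at approximately 1 pm on the second" "day and the check-in procedures in section 6.2 do not need to be repeated". Section 1.5 says: "The study meals and activities will be kept the same between study sessions". The expected mix of sequential and separate stays is not stated.

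Section 12.3 tabulates TIR and the other glycemic measures for each subject. Section 12.4 sets limits of 8, 3 and 8 percentage points on the NAP-UMPC difference in TIR, TBR and TAR, and says that a 5-percent noninferiority hypothesis will be tested without an expectation of significance. Chapter 12 names no group-level estimator and no period term.

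**The concern.** Two things do not fit together. A list of independent draws balances nothing by construction, so the stated aim for age, gender and HbA1c has no visible means of being met. It is also the less useful aim, because each participant serves as their own control.

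The balance that helps a two-period crossover is the number of participants in each sequence. If session 2 tends to differ from session 1 whatever the algorithm, an uneven split passes part of that difference into the plain mean of the NAP-UMPC differences.

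A period effect is plausible mainly in sequential stays. There, session 2 follows the other study algorithm instead of CIQ. It also starts at about 1 PM, some 5 hours before the 6 PM window, whereas in session 1 participants arrive only about 2 hours before it, and the check-in need not be repeated. At stake is how cleanly the group-mean difference can be read against the 12.4 limits.

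**Working it through.** **Inputs.** N = 15 completers with up to 20 recruited (12.2); limits of 8 points and 5 percent, the latter taken as TIR points (12.4). Not in the documents, and assumed here: Bernoulli probability 0.5; paired SD s = 10 points (15 as a variant); period effect p = 2, 5 or 10 points in sequential stays and none in separate stays; share q of stays that are sequential = 1 or 0.5, unrelated to sequence. The protocol has no figure of its own on this point to reproduce: N = 15 rests on experience, not on a formula.

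**1. Sequence split, Binomial(15, 0.5).**
- 8:7: 2 × P(X = 7) = 39.3%
- 10:5 or worse: 2 × P(X ≤ 5) = 30.2%
- 11:4 or worse: 2 × P(X ≤ 4) = 11.8%

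**2. Error for a given split.** Let d be the NAP-UMPC difference, with true value τ. The expected d is τ − p in the NAP-first sequence (size nA) and τ + p in the other (size nB). The plain mean therefore estimates τ + q·p·(nB − nA)/N. At 10:5 and p = 5:
- q = 1: 5 × 5/15 = 1.67 points
- q = 0.5: 2.5 × 5/15 = 0.83 points

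For this alone to use up a limit at 10:5, the average period effect would have to be 5 × 15/5 = 15 points (5-point margin) or 8 × 15/5 = 24 points (8-point limit).

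**3. SD of the estimated mean difference.** Write v = s² + q(1 − q)p². Adjusted means the average of the two sequence-specific mean differences.
- Bernoulli, plain mean: variance (s² + q·p²)/15
- Bernoulli, adjusted: (v/4) × E(1/nA + 1/nB), where the expectation is 0.2897 with both sequences filled
- Blocks at 8:7, plain mean: v/15 + (q·p/15)²
- Blocks at 8:7, adjusted: (v/4) × (1/8 + 1/7)

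Results at s = 10, p = 5:

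| Allocation and estimator | All sequential | Half sequential |
|---|---|---|
| Bernoulli, plain mean | 2.89 | 2.74 |
| Bernoulli, period-adjusted | 2.69 | 2.77 |
| Blocks 8:7, plain mean | 2.60 | 2.67 |
| Blocks 8:7, period-adjusted | 2.59 | 2.67 |

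Most of the gain comes from the blocks. A period term on the Bernoulli list is not a full substitute; with half the stays sequential it is slightly worse than the plain mean.

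Other settings, Bernoulli plain mean to blocks adjusted:
- p = 0: 2.58 to 2.59 (a very small loss)
- p = 2: 2.63 to 2.59 (all), 2.61 to 2.60 (half)
- p = 10: 3.65 to 2.59 (all), 3.16 to 2.89 (half)
- s = 15, p = 5: 4.08 to 3.88 (all), 3.98 to 3.94 (half)

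**4. Completers rather than randomised.** If 20 are randomised 10:10 and a random 15 complete, the all-sequential blocked figures at p = 5 become 2.61 adjusted and 2.67 plain. A 10:5 split among completers then has probability 3%.

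**5. Effect on the 8-point reading of the group mean.** With τ = 0, s = 10, p = 5 and a normal approximation, the chance that the mean lies within 8 points goes from 99.44% to 99.80% (all sequential) or from 99.65% to 99.73% (half).

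**6. If the 12.4 limits are read per participant.** Each participant's own difference carries the full p, in opposite directions by sequence. With τ = 0, s = 10, p = 5 in every stay and a signed limit (UMPC minus NAP below 8), the chance of passing is Φ(0.3) = 62% in one sequence and Φ(1.3) = 90% in the other. The expected share passing is (10 × 62% + 5 × 90%)/15 = 71% at one 10:5 split and 81% at the reverse, against Φ(0.8) = 79% with no period effect. Under an absolute limit the split does not matter, but the share still falls from 58% to 52%.

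**The case against.** The strongest reply is that nothing of consequence turns on this. The protocol calls the glycemic analyses descriptive, says that noninferiority is unpowered, and gives initial system testing as the main purpose. Meals and activities are matched, which removes an obvious source of period effect. The period effect, the paired SD and the share of sequential stays are all assumed here. This stands, and it is why the point is an inexpensive improvement and not a flaw that threatens the trial.

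Second, the protocol speaks of an aim, not a guarantee. A list screened for balance, or draws with covariate-dependent probabilities, would fit the sentence. That is fair: the defect is an unnamed mechanism, and the percentages in step 1 hold for independent draws at 0.5. A reader might infer that the protocol promises balance and fails to deliver it, or that covariate imbalance would confound the comparison. The wording does not support the first, and the within-person design largely answers the second.

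Third, Bernoulli draws are unpredictable, and blocks are less so. The trial has one site, describes no blinding, has study staff switch the algorithm, and lets sessions be cancelled at clinical discretion. In simulated lists of 15, a best guesser who sees all earlier assignments is right about 68% of the time with blocks of 4 and 6, against 50% for Bernoulli draws, and about 6% of assignments are certain. This cost is real. It matters less than in a parallel-group trial, because every participant receives both algorithms and only the order can be guessed.

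A reader might also infer that reading the 12.4 limits per participant avoids the problem, since 12.3 tabulates by subject and 12.4 refers to each participant's day-to-day variability. Step 6 shows the opposite: that reading takes the whole period effect, and neither blocks nor the adjusted estimator removes it from individual differences.

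**Conclusion.** The point holds as a modest one. Section 12.1 pairs Bernoulli draws with a balance aim that they do not serve, leaves sequence balance to chance, and Chapter 12 states no group-level estimator. The result is avoidable noise in an unadjusted group mean: at an assumed paired SD of 10 and a 5-point period effect, blocks with adjustment lower its SD by 0.30 points if all stays are sequential and by 0.07 if half are. At 2 points or less the gain is negligible, and at 10 points it is material (1.06 or 0.27 points).

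It would be tempting to call this a bias for or against NAP, or to say that an uneven split could by itself decide the 12.4 criteria. Neither is supported. The error averages zero over possible lists, and at 10:5 it would take an average period effect of 15 or 24 points to use up a limit. The size of the gain depends wholly on the assumed period effect, paired SD and share of sequential stays. The missing mechanism and the missing estimator do not depend on those assumptions.

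**What to change.** **In 12.1**, replace the Bernoulli sentence with wording such as:

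> Sequence (NAP-UMPC or UMPC-NAP) is assigned 1:1 from a concealed list of permuted blocks of randomly varying size (for example 4 and 6). A replacement takes the next unused slot.

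Delete the age, gender and HbA1c aim, or name the mechanism that meets it (stratification or minimisation, say). Simple blocks will not.

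**In Chapter 12**, state that the group-level NAP-UMPC estimate for TIR, TBR, TAR and the noninferiority analysis is the average of the two sequence-specific mean within-person differences, and that the 12.4 limits apply to that estimate. Report completers and individual differences by sequence and by stay type (sequential or separate).

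**Cost.** A new list, a few sentences and one degree of freedom (14 to 13), with no added participants or visits. Later assignments become more guessable, so the list should be concealed and the block sizes withheld from site staff. Blocks of 4 and 6 give 8:7 in 98% of simulated lists of 15 and 9:6 otherwise, but they balance those randomised, not those who complete. Carryover and differences between stay types are not removed.

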### 853 12.2 Sample Size

854 We use pilot trials to introduce new technologies, test system component interoperability, and  
855 support regulatory approval of larger subsequent studies. Depending on the traceability of the  
856 system to previous established technology or components, the pilots can range from a small 5-  
857 person 3-day trial, such as the one we used to enable the pivotal trial of Control-IQ, to a multi-  
858 center test of pump configurations. In this study, NAP is directly traceable to UMPC in terms of  
859 its functionality; however, its implementation is qualitatively new. Thus, based on our experience,  
860 we estimate that the completion of N=15 (and recruitment of up to 20) CIQ users who will test  
861 NAP vs UMPC during two 18-hour hotel sessions, will be feasible, in terms of first regulatory  
862 approval, and sufficient to test the translation of the existing UMPC into neural-net framework.

### 863 12.3 Outcome Measures

864 The main purpose of this trial is initial system testing and receiving feedback from the participants  
865 regarding system functionality. Thus, we will observe, record, and tabulate any NAP errors that  
866 would inform us whether system fixes would be needed prior to deployment in a subsequent larger  
867 study. We will tabulate technical performance metrics including:

- 868 • Malfunctions requiring study team contact and other reported device issues;
- 869 • Percent time in closed-loop and any other relevant operational modes;
- 870 • Rate of relevant NAP and UMPC failure events and alarms per 24 hours;

871 In addition, descriptive glycemic analyses for certain efficacy measures recommended by a review  
872 written by the sponsor of this study and by the International Consensus on Time-in-Range (TIR),  
873 to which we contributed, will be tabulated for each subject based on CGM data, including:

- 874 • TIR, 70-180 mg/dL (primary outcome)
- 875 • percentage of readings in other ranges, including TBR, TAR, and 70-140 mg/dl;
- 876 • mean glucose; glucose variability measured by coefficient of variation;
- 877 • percentage of readings <54 mg/dl (i.e., level 2 hypoglycemia)
- 878 • percentage of readings >250 and >300 mg/dl (i.e., level 2 hyperglycemia)

## CLINICAL PROTOCOL

879 The technical performance, errors, and glycemic analyses will be also split by time of the day:  
880 daytime vs. night-time.

### 881 **12.4 Criteria for Success**

882 The success criteria will include no critical system errors and the following performance criteria,  
883 which factor in likely inter-day variability for each participant and are consistent with the  
884 recommendations of the International Consensus on TIR:

- 885 • Difference in TIR between NAP and UMPC < 8 percentage points;
- 886 • Difference in TBR between NAP and UMPC < 3 percentage points;
- 887 • Difference in TAR between NAP and UMPC < 8 percentage points;

888 Formal power analysis is not applicable to this pilot study – 5-percent noninferiority hypothesis of  
889 NAP vs UMPC will be tested, but with this sample size a statistically significant result is not  
890 expected. The point of the study is to show feasibility of a neural-net implementation of an  
891 automated insulin delivery algorithm which, if shown, will open possibilities for control strategies  
892 based on machine-learning and artificial intelligence methods.

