104 The concept of AMBC is to enable a pathway towards adaptive AP algorithms which are capable  
105 of learning from a person’s CGM and insulin delivery patterns, and from the patterns of others  
106 stored in databases. The first step towards this concept of the future, is translating a well-  
107 established AP control algorithm, e.g., UMPC into a Data Science “environment,” i.e., creating a  
108 Neural Net adaptation of a model-predictive controller. This protocol intends to test such an  
109 adaptation – a Neural Net AP (NAP) – in a brief study in a well-controlled environment. Studies  
110 to follow will expand this concept further and will add elements of controller adaptation based on  
111 data accumulated in databases, labelled by prefixed “motifs” – a recently established structure of  
112 daily CGM profiles. The latter would allow a finite table-lookup approach to real-time AP control  
113 adaptation; but, this is a subject of future studies. Now we focus on the first step only – translating  
114 a controller into a neural-net environment.

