## CLINICAL PROTOCOL

[figure not shown]
115 *Thus, the only new AID algorithm tested in this study is NAP – a neural-net implementation of the*  
 116 *UMPC – which produces insulin adjustment commands identical (within a small tolerance) to the*  
 117 *original UMPC (see Appendix A-1: Algorithm Description). We should also emphasize that the*  
 118 *two experimental algorithms used in this study, UMPC and NAP, modulate only the basal rate of*  
 119 *insulin delivery. The other components, the Adaptive Bolus Priming System, the Hyperglycemia*  
 120 *Mitigation System, and the Safety System Module dedicated to prevention of hypoglycemia –*  
 121 *remain unchanged from previous studies and are described in IDE # G220204. In particular, the*  
 122 *Safety System has been reviewed by the Agency in virtually all IDEs in the reference list. The*  
 123 *Safety System Module has also been tested for its ability to prevent hypoglycemia in pivotal trials*  
 124 *[IDE#G180053 and IDE#G180053] and in millions of days of routine home use, as part of the*  
 125 *commercial Control-IQ AID device system.*

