### 1.2 Objective and Primary Outcome

127 Pilot test the safety and feasibility of a NAP implementation of an established AP controller –  
 128 UMPC – in a crossover study. The primary outcome is percent TIR (70 to 180 mg/dL) on NAP vs  
 129 UMPC. Secondary outcomes include frequency of hypoglycemia (TBR) and hyperglycemia  
 130 (TAR), as well as other safety and control metrics. We will analyze non-inferiority of NAP  
 131 compared to UMPC, but *this pilot feasibility study is not powered to formally test noninferiority.*

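### Do the section 12.4 success limits need a stated direction, summary measure and interval before they can be applied?

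*Combined protocol and SAP*

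**What the plan says.** Section 12.4 defines success as the absence of critical system errors plus three performance limits: "Difference in TIR between NAP and UMPC < 8 percentage points", "Difference in TBR between NAP and UMPC < 3 percentage points" and "Difference in TAR between NAP and UMPC < 8 percentage points". The lead-in says of these limits "which factor in likely inter-day variability for each participant". A separate paragraph then refers to a "5-percent noninferiority hypothesis of" NAP against UMPC, and adds that statistical significance is not anticipated with this number of participants.

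Elsewhere:
- Section 1.1 describes the work as translating "a controller into a neural-net environment" and says NAP "produces insulin adjustment commands identical (within a small tolerance) to the" original UMPC.
- Section 1.2 says "We will analyze non-inferiority of NAP" relative to UMPC, and in the same sentence that the pilot lacks the power for a formal test.
- Section 12.2 justifies 15 completers by experience, as enough to test the translation. It gives no SD, alpha or power.
- Section 12.3 puts system testing and participant feedback first, calls the glycemic analyses descriptive, and tabulates the measures by subject.

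**The concern.** Higher TIR is good, while higher TBR and TAR are bad. One signed wording therefore cannot limit harm on all three: NAP minus UMPC leaves the TIR line open to a loss, and UMPC minus NAP leaves the TBR line open to added hypoglycemia.

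The cues in the plan also differ. Fidelity to UMPC suggests an absolute difference, noninferiority suggests a directed one, and the remark about variability for each participant could suggest a participant-level rule. The plan does not say whether a point estimate or a confidence bound must meet the limit, or how the 8-point limit relates to the 5-percent hypothesis.

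Because these are the stated success criteria and one concerns the primary outcome, the worry is that the reading could be chosen once the data are known, or that meeting the 8-point limit could be reported as though it showed noninferiority.

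**Working it through.** The plan has no figure of its own to reproduce here. The check asks how far the verdict moves between readings, and which readings the text supports.

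**Direction (no SD needed).** The list of abbreviations defines TBR as below 70, TIR as 70-180 and TAR as above 180 mg/dL, so the three add to 100% and dTIR + dTBR + dTAR = 0. With d = NAP minus UMPC in points, and harm-directed meaning dTIR > -8, dTBR < +3, dTAR < +8:

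| dTIR / dTBR / dTAR | Signed NAP-UMPC | Signed UMPC-NAP | Absolute | Harm-directed |
|---|---|---|---|---|
| -10.8 / +2.9 / +7.9 | pass | fail | fail | fail |
| -7 / +5 / +2 | fail | pass | fail | fail |
| +3.5 / -3.5 / 0 | pass | fail | fail | pass |

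The first row is 0.108 x 1080 = 117 minutes of lost range in an 18-hour session. It lies close to the worst case for its reading: dTIR = -(dTBR + dTAR) > -(3 + 8) = -11. The gap between the signed NAP-UMPC and absolute readings on TIR loss is therefore the band from 8 to 11 points. Under UMPC-NAP the TIR line itself keeps the net rise in TBR plus TAR below 8 points.

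**Summary unit (SD assumed).** Take N = 15 (section 12.2), normal paired differences, equal algorithms, and assumed SDs of 5, 10, 15 and 20 points.

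- Mean within 8 points: 2Φ(8√15/SD) - 1 = >0.999, 0.998, 0.961, 0.879.
- One participant within 8 points: p = 2Φ(8/SD) - 1 = 0.890, 0.576, 0.406, 0.311.
- Expected number of 15 within 8 points: 15p = 13.4, 8.6, 6.1, 4.7.
- All 15 within 8 points: p^15 = 0.175, 0.00026, and below 0.0001 for the last two.

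An all-participants rule would almost always fail two identical algorithms at SD 10 or more. No section states such a rule. The remark about variability explains the size of the limits and does not name a unit.

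**Interval and noninferiority.** The 95% half-width is 2.145 x SD/√15 = 2.77, 5.54, 8.31, 11.08. At SD 10 an observed -7.9 meets the limit, with interval -7.9 ± 5.54, that is -13.4 to -2.4. Suppose 5-percent means a 5-point margin at one-sided 0.025 (both assumed). Noninferiority then needs an observed mean above -5 + 5.54 = +0.54, and power with equal algorithms is about 44%. At one-sided 0.05 power is about 58%. At SD 5 and one-sided 0.025 it would be about 95%, which does not fit the plan's own expectation of no significant result, so the larger SDs are the relevant ones.

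**Which reading the text supports.** A difference between two things that must stay below a limit is ordinarily a magnitude. Three lines worded alike, on measures with opposite good directions, make sense together only as magnitudes. That matches the purpose in sections 1.1 and 12.2, which is whether the neural net reproduces UMPC. For a crossover with 15 completers, the mean within-participant difference is the usual summary. Noninferiority comes in a later, separate paragraph and is not expected to be significant, so success cannot depend on it.

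**The case for a change.** The strongest case for a change is that a section titled as success criteria should be a complete rule. Low power does not excuse an undefined one, the missing words cost nothing, and the pilot is meant to support larger studies. The +3.5/-3.5/0 example has force: NAP spends 0.035 x 1080 = 38 minutes less below range and fails as a magnitude, but passes if the limits bound harm only. Here the two sensible readings disagree.

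Part of this stands. The words absolute and mean are implied and not written, and 5-percent is not identified as a margin or an alpha. Writing them down would be a courtesy to the reader.

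It does not amount to a needed change, for three reasons:
- The choice between absolute and harm-directed limits has a price either way. Absolute limits fail NAP for doing better, and directed limits let it depart from UMPC and still pass. The documents give some support to both.
- The measures are tabulated by subject for both systems, so the size and direction of any difference will be visible whichever word is used.
- A paired interval beside each limit is good reporting, but it does not repair an error. For TBR, which is bounded at zero, with 15 participants it would need care.

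**Conclusion.** The gap in wording is real but does not call for a change. Analysts following the plan would sensibly compare the absolute mean within-participant difference with 8, 3 and 8 points, as a descriptive feasibility check separate from the noninferiority analysis. On that reading, equal algorithms meet the TIR limit with probability 88% to more than 99.9% for assumed SDs of 20 down to 5.

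The signed readings are the least natural. Under NAP minus UMPC, what would slip through is limited to TIR losses of 8 to 11 points, a bound that needs no SD. The very low pass rates belong to an all-participants rule that the plan does not contain. Section 12.3 ties the need for system fixes before a larger study to tabulated NAP errors, and no section makes these three limits a stopping or go/no-go rule.

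The conclusion rests on the stated purpose of reproducing UMPC and on the descriptive status of the glycemic analyses. If the same limits were carried into a confirmatory trial, direction, summary and margin would have to be written out.
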